9.4 Documentation

Attention is to be paid to the occurrence of AEs at all stages of the examination. Thus, the patient should be closely observed by the investigator both during and after the treatment. The recording phase for AEs will start with the first study drug administration and will end the last day of the follow-up period. AEs related to hematological or renal toxicity which are still present at the end of the follow-up period will be followed up until complete resolution as assessed by the investigator. Any adverse events have to be documented in detail as indicated on the E-CRF. The following information is required:

- The date and **time of onset** of any AEs
- The **duration** (the entire duration of an event or symptom, calculated from date of onset and date of end)
- The maximum **intensity** (mild, moderate or severe; for definitions, see below).
- The **drug relationship** of the AE to the investigational product (for definitions, see below)
- Any **study drug action taken** and any other **action taken** by the investigator to resolve the adverse events (entered in free text)
- The **outcome** of the adverse event (recovered completely, recovered with residual effects, continuing).
- An assessment of the **seriousness** of the event will be made by the investigator.

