Study endpoints	
Primary endpoint:
 
 • Target lesions tumour response 
Secondary endpoints:
 
 • Overall tumour response • Liver specific progression-free survival post ¹⁶⁶Ho-RE • Non-liver specific progression-free survival • Overall survival • Toxicity • Quality of life • Performance status • ^{99m}Tc-MAA and ¹⁶⁶Ho-PLLA-MS scout and therapy dose SPECT/CTs comparison • ¹⁶⁶Ho-PLLA-MS scout dose and total dose MRI comparison • ¹⁶⁶Ho-PLLA-MS scout dose and total dose PET/CT comparison
Duration of treatment	The study consists of a screening phase of approximately 2 weeks followed by a treatment phase of approximately 2-3 weeks. Patients will be followed until liver specific tumour progression or death has occurred, to a maximum of 12 months.
Methodology	A first cohort of 30 patients will be treated with ¹⁶⁶ Ho-RE. After the first cohort, up to 3 additional cohorts of 6 patients will be treated with ¹⁶⁶ Ho-RE. The total number of patients treated in the HEPAR II trial will therefore be at least 30 and at most 48 patients, depending on the observed number of responses. Early termination at a response interim analysis (after 30, 36 or 42 patients) is determined by pre-defined boundaries on the number of observed responses. The boundary in favour of treatment effect may be crossed before 30 patients are reached, but then the study will continue to at least 30 patients to allow estimation of the key secondary endpoints.
Number of study centers	Single center (UMC Utrecht).
Adverse events	All adverse events will be recorded throughout the study.
Inclusion period	Mar 2012 – Aug 2015
Analysis	
Full analysis will be performed after the last patient's last visit. The primary analysis will be to estimate the target lesions tumour response rate (with 95% confidence interval, adjusted for early stopping if indicated). Secondary analysis will be similar estimations of response rates or estimated survival curves (cumulative incidences). Primary and secondary analyses will be based on the Full Analysis Set; analyses on the Per Protocol Set will also be performed and reported.
 
The study will be monitored with stopping boundaries on the number of observed responses. Early termination may occur as a consequence after 30, 36

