5.2.2 Pretreatment visit

Patients will be hospitalized on the evening before the day of the pretreatment angiography. They will be discharged approximately 24 hours after the intervention unless complications occur. The screening visit can coincide with the pretreatment and treatment visit, if so, duplicate procedures need not be performed. If the treatment is shortly after the pretreatment, the hospital stay can be extended for the duration of that visit. During this visit, the following must be documented and reviewed as a part of the study:

- Inclusion and exclusion criteria
- Physical examination (incl. vital signs)
- Pregnancy test for women of childbearing age
- WHO performance assessment
- Concomitant medication
- Monitoring of occurrence of (serious) adverse events
- Laboratory examination type A (blood)
- Pretreatment angiography, administration of ^{99m}Tc -MAA
- ^{99m}Tc -MAA SPECT/CT

On day 0, the patient is subjected to an angiography of the upper abdominal vessels. At least the celiac axis and superior mesenteric artery are visualised, followed by coiling of relevant vessels, especially branches of the celiac axis supplying non-target organs. This procedure will be performed by a skilled and trained interventional radiologist. The catheter is introduced using the Seldinger technique. Prior to the procedure the patient is offered a tranquilizer. Premedication consists of proton pump inhibitors (pantoprazol 1 dd 40 mg), starting at the day of the intervention. Proton pump inhibitors are prescribed to the patients to be used until 3 months post ^{166}Ho -RE.

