7.3.1 Spurious aneurysm and hematoma

As a complication of arterial catheterization in the groin, a false aneurysm (spurious aneurysm/pseudoaneurysm) may develop at the vascular access site within a few days after the procedure. This can be suspected in case of local pain and swelling in the groin, and is diagnosed with the use of ultrasound. In most cases, ultrasound-guided compression will be effective. Pseudoaneurysms less than 2 cm in size can be managed conservatively and monitored by serial imaging to confirm spontaneous resolution. First-line treatment consists of injection of bovine thrombin [37]. If the aneurysm is becoming very large and threatens or causes skin necrosis, or is expanding rapidly as it may be infected, surgical intervention should be performed. In case of vascular access site hematoma, conservative treatment is advised, because hematomas are known to resolve spontaneously in most cases within days.

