9.2.1 Investigational medical device

Medical device (Ho-166 poly lactic microspheres) being assessed for safety or performance in this clinical investigation (HEPAR-II)

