9.2.3 Adverse events (AEs)

Adverse events are defined as any untoward medical occurrence, unintended disease or injury or any untoward clinical signs (including an abnormal laboratory finding) in subjects, users or other persons whether or not related to the investigational device (Ho-166 poly lactic acid microspheres). This also includes events related to the procedures involved (any procedure specified in the clinical investigation plan).

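### Section 9.4 opens adverse event recording at the first study drug administration, which contradicts the protocol's own requirement to capture events from the earlier pretreatment angiography and coiling

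*Protocol*

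**What the plan says.** Section 9.4 (Documentation) fixes the start of data capture: "The recording phase for AEs will start with the first study drug administration". It ends on the last day of follow-up. The same section opens more broadly: "Attention is to be paid to the occurrence of AEs at all stages of the examination".

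Section 9.2.1 (Investigational medical device) names the product: "Medical device (Ho-166 poly lactic microspheres) being assessed for safety or performance in this clinical investigation". Section 5.2.3 places its first administration, the scout dose, at the treatment visit.

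The first invasive step is earlier. Section 5.2.2 says: "On day 0, the patient is subjected to an angiography of the upper abdominal vessels". Coiling follows, and then the technetium-99m albumin dose. Section 5.2.2 also lists "Monitoring of occurrence of (serious) adverse events" among the items to be documented at that pretreatment visit, and Table 2 marks the same item in its pre-treatment column.

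Section 9.2.3 (Adverse events) says of the definition: "This also includes events related to the procedures involved (any procedure specified in the clinical investigation plan". The adverse events row of the Summary says: "All adverse events will be recorded throughout the study". Section 9.3.1 requires every event that the patient reports or the staff observe to be recorded, and gives no start date.

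**The concern.** The start of the recording phase decides which events enter the E-CRF. An analysis plan cannot recover an event that was never entered, so this has to be settled in the protocol.

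Section 7.3 lists technique-related complications that either angiography could cause: access-site haematoma or false aneurysm, puncture-wound infection, arterial dissection or inadvertent embolization, contrast-induced renal insufficiency and thromboembolism. On timing, 7.3.1 says a false aneurysm "may develop at the vascular access site within a few days after the procedure". After the first angiography that would often fall before the scout dose.

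Toxicity is a secondary objective. Section 10.2 summarises it as counts and percentages, the IDMC reviews it every 3 months, and section 12.8 intends the data for a CE-marking application. If one member of staff follows 9.4 and another follows Table 2, similar events are handled differently and the procedural counts are too low.

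**Working it through.** No arithmetic is at issue beyond the length of the interval, so the check sets the passages side by side.

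**1. What counts as study drug.** The term is not defined in this device protocol. Section 9.2.1 names only the holmium-166 microspheres as the device under investigation. Section 9.4 asks for each event's relationship to the investigational product, and 9.4.2 defines that relationship as one to the holmium-166 microspheres. The natural reading is therefore the scout dose, the first microspheres given.

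**2. When that is.** Section 5.2.3 puts the treatment visit about 1 week (7 days) after the first intervention, and at most 3 weeks (3 × 7 = 21 days). Section 5.2.2 allows treatment soon after pretreatment within one extended hospital stay, so the interval can be shorter than 7 days.

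**3. What each place requires for the period between the first angiography and the scout dose.**

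| Place in the protocol | Are events in this period captured? |
|---|---|
| 9.4, start of recording | No |
| 9.4, opening sentence | Yes, all stages |
| 9.2.3, Adverse events | Yes, events of protocol procedures are included |
| 5.2.2, pretreatment visit | Yes, monitoring is a required item |
| Table 2 | Yes, marked at pre-treatment (blank at screening) |
| 9.3.1 | Yes, no start date |
| Summary | Yes, throughout the study |
| 9.3.4 and 9.3.5 | Yes for serious events, no start date |

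One sentence in 9.4 stands against all the others.

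**4. The alternative reading.** Suppose the technetium-99m albumin counts as study drug. Recording then opens on day 0, and a false aneurysm appearing days later is captured. But section 5.2.2 gives that agent only after angiography and coiling have succeeded. Events before or during those steps, such as a dissection or a contrast or premedication reaction, still precede the start. The gap narrows and does not close.

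**5. Who is affected.** Patients who receive the therapy dose have already had the pretreatment angiography, so the gap applies to patients inside the Full Analysis Set. Patients excluded under 5.2.2 for lung shunt or uncorrectable extrahepatic deposition never receive holmium-166, so for them the literal 9.4 recording phase never opens. Section 8.2.1 leaves patients without the therapy dose out of every analysis in any case. That is a separate matter.

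**The case against.** The best reply is that 9.4 is outnumbered. Table 2, 5.2.2, 9.3.1, the Summary and the opening of 9.4 itself all point to capture, and staff already have to ask about events at the pretreatment visit. On this view the sentence is loose wording and little is lost. It is right that the protocol shows a conflict of rules and does not show that events will be missed. It does not remove the conflict, because 9.4 is the section that states when the recording phase begins.

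A second reply is that the serious complications are protected. This stands to a large extent. Section 9.3.4 makes any serious event reportable, 9.3.5 sends it to the ethics committee and the IDMC, and 8.4 has the IDMC receive reports on all SAEs, none of these with a start date. A reader might infer that the IDMC would not see serious events of the first angiography. The documents do not support that.

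Three other stronger readings also fail:

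- **Onset dates.** A reader might think that an event still open at treatment could have no valid onset date. Section 9.4 asks for the onset date of any event, and nothing bars one before the scout dose.
- **A fixed gap of 7 to 21 days for every patient.** The interval can be shorter, so a false aneurysm need not always arise inside it.
- **Two angiography sessions for every patient.** Patients found ineligible after the pretreatment scan do not go on to a treatment angiography.

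Finally, the primary endpoint, stopping boundaries and sample size are untouched. That limits the weight of the point without answering it.

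**Conclusion.** Wrong as written: an internal contradiction. Read with the device definition, the 9.4 start point leaves out the interval from the pretreatment procedures to the scout dose, usually about 7 days, at most 21, and sometimes less. The definition, the schedule, the general recording rule and the Summary all include it.

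The consequence is conditional. If 9.4 is followed, adverse events of the first angiography, coiling, contrast and premedication can be left out of the E-CRF and the safety summaries. The exposure is chiefly to non-serious events. The direction is towards understating procedural harm. The size cannot be calculated, because the protocol gives no complication rate for the first angiography considered separately.

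The length of the interval assumes that study drug means the holmium-166 microspheres. The contradiction itself does not depend on that reading.

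**What to change.** In 9.4, replace the start of the recording phase so that it opens no later than the start of the first protocol-specified procedure at the pretreatment visit. Replace the undefined term for study drug in that sentence with the named procedure. The text then agrees with Table 2, 5.2.2, 9.2.3 (Adverse events), 9.3.1 and the Summary.

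A start at informed consent would not agree with Table 2 as it stands, because its adverse event row is blank at screening. That choice would need a change to the table as well.

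The cost is one sentence. Monitoring is already required at the pretreatment visit, so no visit, test or procedure is added, and clinical management is not touched.

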9.4.1 Intensity

Toxicities listed in the NCI CTCAE v4.0 are graded on a scale of 0 to 4. If a specific adverse event is not included in the toxicity scale, the investigator is to classify its intensity according to the following definitions:

Table 6. Intensity grading of AEs not described in NCI CTCAE v4.0

Intensity	Definition
Mild	The patient is aware of signs or symptoms, but they are easily tolerated. Usually does not require additional therapy or discontinuation of study treatment.
Moderate	The signs and symptoms are sufficient to restrict, but do not prevent usual activity; possibly requires additional therapy but usually does not require discontinuation of study treatment.
Severe	The patient is unable to perform usual activities and usually requires discontinuation of study treatment.

9.4.2 Treatment relationship

The investigator will be asked whether an AE is related to the administration of ^{166}Ho -PLLA-MS, or whether he is not capable to define a clear relationship to the study device. The investigator will also be asked whether an AE is related to inadvertent deposition of the microspheres in organs other than the liver, and should therefore be classified as technique related.

Table 7. categories of treatment relationship of AEs

Categories	Definition
None	The time course between administration of ^{166}Ho -PLLA-MS and occurrence or worsening of the adverse event rules out a causal relationship and/or another cause is confirmed and no indication of involvement of ^{166}Ho -PLLA-MS in the occurrence/worsening of the adverse event exists.
Unlikely	The time course between administration of ^{166}Ho -PLLA-MS and occurrence or worsening of the adverse event makes a causal relationship unlikely and/or the known effects of ^{166}Ho -PLLA-MS or of the substance class provide no indication of involvement in occurrence/worsening of the adverse event and another cause adequately explaining the adverse event is known and/or regarding the occurrence/worsening of the adverse event a plausible causal chain may be deduced from the known effects of ^{166}Ho -PLLA-MS or the substance class, but another cause is much more probable and/or another cause is confirmed and involvement of ^{166}Ho -PLLA-MS in the occurrence/worsening of the adverse event is unlikely.
Possible	Regarding the occurrence/worsening of the adverse event, a plausible causal chain may be deduced from the pharmacological properties of ^{166}Ho -PLLA-MS or the substance class, but another cause just as likely to be involved is also known or although the physical properties of ^{166}Ho -PLLA-MS or the substance class provide no indication of involvement in the occurrence/worsening of the adverse event, no other cause gives adequate explanation
Probable	The physical properties of ^{166}Ho -PLLA-MS or of the substance class and/or the course of the adverse event after dechallenge and, if applicable, after rechallenge and/or specific tests suggest involvement of ^{166}Ho -PLLA-MS in the occurrence/worsening of the adverse event, although another cause cannot be ruled out.
Definite	The physical properties of ^{166}Ho -PLLA-MS or of the substance class and the course of the adverse event after dechallenge and, if applicable, after rechallenge and specific tests indicate involvement of ^{166}Ho -PLLA-MS in the occurrence/worsening of the adverse event and no indication of other causes exists.
Unclassified [only used for SAE]	The available information is not sufficient for causality assessment.

9.5 Follow-up of adverse events

All adverse events will be followed until they have abated, or until a stable situation has been reached, or until completion of study follow up period. Depending on the event, follow up may require additional tests or medical procedures as indicated, and/or referral to the general physician or a medical specialist.

10. STATISTICAL ANALYSIS

Two sets of study data will be evaluated: the Full Analysis Set (FAS) and the Per Protocol Set (PPS). The FAS is defined as the set of data generated from all included patients who received the therapy dose. The PPS is defined as the set of data generated from the included patients who complied with the protocol up to at least 3 months of follow-up. All analyses will be performed for the FAS. Analyses to assess tumour response and explore and understand the direct effects of therapy will be based on the PPS.

The primary analysis will be the evaluation of the number and percentage of patients with target lesions tumour response, according to the group sequential decision criteria as given in chapter 3. In addition, the estimated response percentage and appropriate 95% confidence interval will be presented. Further description in numbers and percentages with complete response, partial response, stable disease and progressive disease will be provided. For the tumour response decision, this analysis is primarily based on the PPS set as defined above. However, the analysis based on the FAS will also be performed. In that case, a conservative imputation on target lesions tumour response will be done for those patients that did not reach their 3 months of follow-up (e.g., if a patient died before 3 months or stopped because of disability reasons it will be classified as failure).

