3. STUDY DESIGN

Study type	Interventional
Study design	Interventional, treatment, one group, phase II study with a medical device.
Study start date	Mar 2012
Estimated study completion date	Aug 2015

This phase II study comprises a group of at least 30 and at the most 48 patients suffering from liver metastases of primary cancers of miscellaneous origin. Patients who will be included have hepatic metastases not amenable for surgical resection or further systemic treatment. A liver absorbed dose of 60 Gy will be used in each patient in this study. A radiation dose of 60 Gy equates to 3.8 GBq ^{166}Ho /kg liver tissue.

The primary outcome is target lesions tumour response at three months follow-up. For this study, this is defined as: 1) complete response on CT at 3 months, or 2) partial response on CT at 3 months or 3) stable disease on Computed Tomography (CT) at 3 months (see chapter 8.3.1 Definition of treatment success).

This single arm open label study will have a sequential design as follows. Patients will be followed for target lesions tumour response up to 12 months or less if liver specific tumour progression or death occurs. Interim analyses for tumour response achieved are based on sequential decision boundaries. Stopping boundaries are determined such that an overall one-side alpha of at the most 0.05 is maintained in case the true tumour response is 20% ($p_0 \equiv 20\%$). Early termination at a response interim analysis (after 30, 36 or 42 patients) is determined by pre-defined boundaries on the number of observed responses. The boundary in favour of treatment effect may be reached or crossed before 30 patients are reached, but then the study will continue to at least 30 patients to allow estimation of the key secondary efficacy endpoints. Early stopping for proven efficacy can only occur after the first 30 patients are evaluated. Boundaries for early stopping due to futility, i.e. absence of a relevant effect on tumour response, are also included, and are in effect even before the number of 30 patients is reached. The sequential design with boundaries as given in Table 1 will have a power of 90% to reach a positive tumour response decision in case the true target lesions tumour response is 40% ($p_1 \equiv 40\%$). The exact overall one sided type I error is 4.5% [28].

Table 1 Stopping boundaries for early termination at interim analysis.[28] Stopping is indicated if the observed number of responses is at the boundary or beyond.

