8.2.1 Replacement of withdrawn patients

All patients registered in the study will be accounted for. Patients who do not receive the therapy dose of ^{166}Ho -PLLA-MS will be replaced by another patient, and will not be included in any of the analyses. Based on the (sequential) design and criteria, recruitment and treatment will continue for the first cohort until 30 patients can be evaluated for tumour response. All patients that received ^{166}Ho -RE will be analysed for safety and secondary endpoints, regardless of their availability for tumour response evaluation. For example, a patient that drops out of the study 2 months post treatment will be evaluated for safety and secondary endpoints. However, this patient does not count as one of the 30 patients in whom tumour response needs to be evaluated in the first cohort. Therefore, the patient needs to be replaced. Consequently, if the study continues beyond 30 patients, recruitment will continue in cohorts of 6 patients that can be evaluated for tumour response.

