8.3.2 Determination of ineffective therapy

Therapy for an individual patient is regarded ineffective if target lesions tumour response assessment at 3 months indicates progressive disease according to RECIST 1.1 or if death occurs within this period.

Early termination of the study for lack of efficacy (futility) will be guided by the lower group sequential boundary on the number of patients with treatment success (see 8.3.1). Advice to stop early will be given by the Independent Data Monitoring Committee, that may include other considerations (safety) as well.

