8.4 Independent Data Monitoring Committee (IDMC)

An IDMC is established. The IDMC is an independent group comprising internal members (from within the UMCU) and external members. This phase II study is open label and patients are individually closely monitored for safety, as was done in the HEPAR I study. The main objective is to decide whether or not to embark on a larger phase III trial. Hence it was considered adequate to establish an IDMC with both (independent) internal UMCU members as well as an external member. In case of a future phase III trial, a fully external IDMC is strongly recommended. The IDMC includes the following members:

- Dr. [name], Meander Medical Center Amersfoort; nuclear medicine physician
- Dr. [name], University Medical Center Utrecht; gastro-enterologist
- Dr. [name], Albert Schweitzer ziekenhuis; interventional radiologist
- Dr. [name], Julius Center Health Sciences and Primary Care Utrecht; biostatistician

The IDMC will analyse preliminary study results on tumour response after the first 30 patients who are amenable for tumour response assessment at 3 months (i.e. PPS), and every 6 patients who are amenable for tumour response assessment at 3 months thereafter (see Table 5). Waiting for the three-month follow-up of all 30/36/42/48 patients is only required if, based on the available follow-up in the other patients, it remains uncertain whether the stopping boundaries will be reached.

The IDMC analyse preliminary study results on safety as well (see Table 5). In contrast to the tumour response analyses, the safety analyses will include all patients that received treatment within a time span of 3 months (regardless of their availability for tumour response assessment, i.e. FAS), and therefore, these reviews may not run in sync with the IDMC tumour response analyses. Patient inclusion and treatment may continue during IDMC safety analyses. In its safety analyses, the IDMC will consider specifically the reasons and potential consequences on treatment benefit of the patients that discontinued before the 3 months assessment. The IDMC will receive reports on a regular basis on all SAEs reported for this trial and a complete summary safety report for each safety analysis. The IDMC will work according to the IDMC charter (see Appendix VIII) Recruitment will not be interrupted unless otherwise requested by the IDMC Chairman.

The responsibilities of the IDMC include:

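### The protocol contradicts itself on which patients drive the go/no-go decision, and the set it applies Table 1 to leaves out treated patients who die or leave before 3 months

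*Protocol*

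**What the plan says.** **Deciding set.** The Summary (Analysis) states: "Primary and secondary analyses will be based on the Full Analysis Set; analyses on the Per Protocol Set will also be performed and reported". Section 10 defines the FAS as all included patients who received the therapy dose, and the PPS as those who complied with the protocol to at least 3 months. It says that all analyses will use the FAS, but then adds: "For the tumour response decision, this analysis is primarily based on the PPS set as defined above". Section 8.4 schedules the first response review by the Independent Data Monitoring Committee (IDMC) "after the first 30 patients who are amenable for tumour response assessment at 3 months (i.e. PPS"), and the footnote to Table 5 repeats that the PPS is evaluated primarily.

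**Early loss.** Section 8.2.1 gives the example of a patient who drops out 2 months after treatment: "this patient does not count as one of the 30 patients in whom tumour response needs to be evaluated", and must be replaced. Section 8.3.2 regards therapy as ineffective if the 3-month assessment shows "progressive disease according to RECIST 1.1 or if death occurs within this period". Section 10 imputes failure for early death or a stop for disability, but only in the additional FAS analysis.

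**Number treated.** The Summary (Methodology) and section 2 limit the patients treated to 48.

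**Error rates.** Section 3 sets the boundaries so that "an overall one-side alpha of at the most 0.05 is maintained in case the true tumour response is 20"%. It continues: "The exact overall one sided type I error is 4.5"%, with 90% power at 40%.

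**The concern.** These passages cannot all govern one primary analysis. A patient who dies at 2 months is a failure under section 8.3.2, lies outside the PPS as section 10 defines it, and counts as a failure only in an analysis that does not decide the trial.

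Membership of the PPS depends on what happens after treatment. If those who die or leave early are mostly failures, the success rate in the deciding set exceeds the rate among treated patients. The boundaries then no longer hold the stated error for the treated population. Section 8.4 says that the trial's main purpose is to decide whether to go on to phase III, so a positive decision could rest partly on failures having been replaced.

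Replacement after the therapy dose also means that any such loss, in a trial that runs to the last look, takes the number treated above 48.

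**Working it through.** **Inputs.** From section 3 and Table 1: looks at 30, 36, 42 and 48; lower boundaries 5, 6, 7, 15; upper boundaries 11, 13, 14, 16; stopping at the boundary or beyond; null rate p0 = 20%; alternative p1 = 40%. Section 3 says that futility limits also apply before 30 patients, but Table 1 lists none, so none are used. The protocol gives no rate of loss between treatment and 3 months. The range 5% to 20% is an assumption.

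**Step 1: reproduce the stated figures.** Exact binomial recursion over the four looks, summing the probability of first reaching the upper boundary at each:

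- at 20%: 0.0256 + 0.0048 + 0.0113 + 0.0035 = 0.0452
- at 40%: 0.7085 + 0.0694 + 0.0899 + 0.0301 = 0.8979

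This agrees with the stated 4.5% and 90%. Treating the futility boundaries as non-binding changes the first figure only to 0.0453.

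**Step 2: apply the rule to a selected set.** Let the success rate among all treated patients be 20%, d the fraction lost and replaced before 3 months, and s the success rate that those lost would have had. The rate in the deciding set is

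q = (0.20 − d × s) / (1 − d).

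For d = 10% and s = 0, q = 0.20 / 0.90 = 0.2222. Running q through the same recursion gives the probability of a positive decision:

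| Loss d | q (s = 0) | P(positive), s = 0 | q (s = 10%) | P(positive), s = 10% | P(positive), s = 20% |
|---|---|---|---|---|---|
| 5% | 0.2105 | 6.5% | 0.2053 | 5.4% | 4.5% |
| 10% | 0.2222 | 9.3% | 0.2111 | 6.6% | 4.5% |
| 15% | 0.2353 | 13.3% | 0.2176 | 8.1% | 4.5% |
| 20% | 0.2500 | 18.9% | 0.2250 | 10.1% | 4.5% |

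With s = 20%, loss is unrelated to outcome, q stays at 0.20, and nothing is inflated.

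**Step 3: number treated.** Reaching 48 evaluable patients needs 48 / (1 − d) treated: about 51 at 5% loss, 53 at 10%, 56 at 15% and 60 at 20%.

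**Step 4: power if losses count as failures.** If 40% is the rate among all treated patients, power stays at 89.8%. If 40% holds only among evaluable patients, the all-treated rate is 0.40 × (1 − d):

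| Loss d | All-treated rate | Power |
|---|---|---|
| 5% | 0.38 | 84.1% |
| 10% | 0.36 | 76.5% |
| 15% | 0.34 | 67.1% |
| 20% | 0.32 | 56.3% |

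**The case against.** Four arguments can be made for the plan.

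1. **The null rate may refer to evaluable patients.** Section 3 speaks only of the true tumour response, and sections 8.2.1 and 8.4 openly count evaluable patients. For that parameter the error remains 4.5%. This stands: the stated error is not miscalculated. But the protocol never says which population is meant, and the Summary and section 8.3.2 point to all treated patients.

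2. **The replacement of deaths is not spelled out.** The example in section 8.2.1 is a drop-out, and the withdrawal reasons in section 8.2 do not include death. Section 8.3.2 stands under the heading on premature termination and could be read as governing the boundary count. This too stands in part, as an ambiguity. Section 10 points the other way, since it imputes failure for death only in the FAS analysis.

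3. **There are safeguards.** A FAS analysis with failure imputation is planned. Section 8.4 has the IDMC weigh the reasons for early discontinuation in its safety reviews and take all data into account when it advises. The conservative result would therefore be visible. None of this changes the set on which the boundary is applied.

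4. **Early loss may be small.** Entry requires a life expectancy of at least 12 weeks and WHO status 0 to 2. That is fair, and it is why the size can be given only as a range. Twelve weeks is, however, about the time of the assessment, so some loss is plausible.

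A reader might also infer that patients who progress early are removed. The Summary says "Patients will be followed until liver specific tumour progression or death has occurred", up to 12 months, and section 8.1.2 allows an unscheduled CT when progression is suspected. Such a patient might then have no 3-month assessment. No passage says that this patient is excluded, and an unscheduled CT is permitted by the protocol. It is a gap to close, and the point does not rest on it.

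**Conclusion.** The point holds on the text alone in three respects. The Summary and sections 8.4 and 10 name different deciding sets. Early death is a failure in section 8.3.2 but falls outside the PPS that decides. Replacement after treatment conflicts with the limit of 48 treated patients.

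The effect on the type I error is conditional. It requires that p0 refers to all treated patients and that those lost fare worse than the rest. Under those conditions the direction is anti-conservative. The 5% limit is already passed at 5% loss, even if 10% of those lost would have succeeded (5.4%).

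A reader might conclude that the error is inflated several-fold. The documents do not support that as a fact: a threefold rise needs about 15% loss with every lost patient a failure (13.3% / 4.5% = 2.9). At 5% to 10% loss the factor is 1.4 to 2.1 on that same worst case, and less otherwise.

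**What to change.** Reconcile the Summary and sections 8.2.1, 8.3.2, 8.4 (with Table 5 and its footnote) and 10 as follows:

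- Apply Table 1 to the first 30, 36, 42 and 48 consecutive patients who received the therapy dose (FAS).
- Count death, withdrawal or a missing 3-month assessment as failure.
- State that a documented target-lesion progression before 3 months counts as failure.
- Replace nobody after the therapy dose, which also restores the limit of 48 treated patients.
- Keep the PPS analysis as a sensitivity analysis.
- State in section 3 that p0 and p1 refer to all treated patients.

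The type I error is then 4.5% for the population treated, whatever the loss rate.

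The cost is more than an amendment of wording. The reported success rate will be less favourable. If 40% was meant among evaluable patients only, the stated 90% power no longer applies (76.5% at 10% loss, for instance), and it should be restated on the all-treated basis with the assumed loss rate given, or the design re-derived.
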